7.9 Study Product Discontinuation/Early Termination Visit

Study product discontinuation and early termination evaluations will be performed as described below. Women who must discontinue taking the study product, for reasons described in section 5.3.3.2, before the end of the study-defined treatment period, will be asked to stay in the study to be followed on study/off treatment until study completion. Women who terminate their participation in the study early will be asked to have one final study visit but could return to be followed on study/off treatment until study completion if circumstances of the termination change.

1. Staff will review the memory aid with the participant if the participant declines to return for follow-up visits. The participant will be asked about symptoms, concomitant medications and any medical problems since the last visit, which will be recorded on the appropriate CRF. The participant will be asked to provide exact dates and times of the study product administration.
2. Medical, gynecological and sexual history to include assessment of STI and HIV risk
3. Symptom-directed physical and pelvic examination by a study physician or nurse that will include vital signs, including temperature, and examination of respiratory and cardiovascular systems, as well as assessment of symptoms and adverse events
4. The pelvic examination will be conducted in the following order:
 - a. Examination of the external genitalia
 - b. Speculum insertion and examination of vagina, fornices and cervix with naked eye. Water will be used to ease speculum insertion. No lubricant should be used as it could contain chlorhexidine which may kill *Lactobacillus*.
 - c. Vaginal pH
 - d. Vaginal swab for wet mount taken from the posterior fornix for yeast vaginitis and clue cells and for amine test (whiff test)
 - e. Vaginal swab for Gram stain (Nugent scoring system)
 - f. Vaginal swabs (no more than two) for storage and future identification of vaginal bacteria, and possible multiomic (e.g. proteomics, metabolomics, etc.) testing
 - g. If indicated, cervical (or vaginal) swab for nucleic acid amplification of *N. gonorrhoeae*, *C. trachomatis*, and *T. vaginalis*
 - h. Other tests as deemed necessary by the site investigator in response to symptoms presented at this visit
5. If indicated, clean catch urine dipstick; urinalysis if abnormal results indicate
6. If indicated, urine β hCG pregnancy test
7. All clinical and laboratory findings at the time of the evaluation will be recorded on the CRF. These findings will include observations present on the pelvic exam such

- as genital findings including location; presence or absence, and character of vaginal or cervical discharge or lesions; and results of any on-site tests.
8. Applicators used since the last study visit will be collected. Any remaining unused applicators will also be collected.
 9. Administer acceptability questionnaire
 10. Dispense condoms to subjects who discontinue study product but remain in follow up.
 11. If the clinician suspects the participant developed an STI since the last visit, appropriate tests will be conducted and if needed the woman will be referred to standard of care treatment in compliance with current CDC STD Treatment Guidelines.

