7.10 Unscheduled Visit

An unscheduled visit following a participant's request or the site investigator's recommendation should be recorded on the appropriate CRF. The following procedures and assessments may be performed at the unscheduled visit:

1. Staff will review the memory aid with the participant. The participant will be asked about symptoms, concomitant medications and any medical problems since the last visit, which will be recorded on the appropriate CRF. Additionally, the participant will be asked to provide exact dates and times of the study product administration.
2. Medical, gynecological and sexual history to include assessment of STI and HIV risk
3. Symptom-directed physical and pelvic examination by a study physician or nurse that will include vital signs, including temperature, and examination of respiratory and cardiovascular systems, as well as assessment of symptoms and adverse events
4. The pelvic examination will be conducted in the following order:
 - a. Examination of the external genitalia
 - b. Speculum insertion and examination of vagina, fornices and cervix with naked eye. Water will be used to ease speculum insertion. No lubricant should be used as it could contain chlorhexidine which may kill *Lactobacillus*.
 - c. Vaginal pH
 - d. Vaginal swab for wet mount taken from the posterior fornix for yeast vaginitis and clue cells and for amine test (whiff test)
 - e. Vaginal swab for Gram stain (Nugent scoring system)
 - f. Vaginal swabs (no more than two) for storage and future identification of vaginal bacteria, and possible multiomic (e.g. proteomics, metabolomics, etc.) testing
 - g. Vaginal swabs for *L. crispatus* identification with qPCR
 - h. If indicated, cervical (or vaginal) swab for nucleic acid amplification of *N. gonorrhoeae*, *C. trachomatis*, and *T. vaginalis*
 - i. Other tests as deemed necessary by the site investigator in response to symptoms presented at this visit
5. If indicated, clean catch urine dipstick; urinalysis if abnormal results indicate
6. If indicated, β hCG pregnancy test
7. All clinical and laboratory findings at the time of the evaluation will be recorded on the CRF. These findings will include observations present on the pelvic exam such

- as genital findings including location; presence or absence, and character of vaginal or cervical discharge or lesions; and results of any on-site tests.

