	Vaginal swab for qPCR (L. crispatus identification)		X	X	X	X			X	X	X	X
Other Procedures	Acceptability questionnaire	X				X					X	X
	Staining of used applicators			X*								
	Telephone interview						X	X				

(X) if indicated
X* per site discretion

**APPENDIX B
DIVISION OF AIDS TABLE FOR GRADING THE SEVERITY OF
ADULT AND PEDIATRIC ADVERSE EVENTS PUBLISH DATE: DECEMBER 2004**

**Addendum 1
Female Genital Grading Table for Use in Microbicide Studies**

INDIVIDUAL SIGNS/SYMPTOMS				
PARAMETER	GRADE 0 NORMAL	GRADE 1 MILD	GRADE 2 MODERATE	GRADE 3 SEVERE
GENERAL				
Odor	No complaint	Mild-moderate unpleasant odor	Severe unpleasant odor	NA
PAIN AND TENDERNESS (Specify Area: Vulvar/Perineum, Vagina, Cervix (including cervical motion tenderness), Uterus, Adnexae, Pelvic/Lower Abdominal, or Ovulatory)				
*Note – if both pain and tenderness are present, only report the one with the most severe grade				
Pain* ¹	None	Pain causing no or minimal interference with usual social & functional activities	Pain causing greater than minimal interference with usual social & functional activities or the need for non-narcotic medication	Pain causing inability to perform usual social & functional activities or the need for narcotic medication OR hospitalization (other than emergency room visit) indicated
Tenderness* ¹	None	Mild tenderness	Moderate tenderness	Severe tenderness
Dyspareunia (pain with sexual activity)	None	Pain causing no or minimal interference with sexual function	Pain causing greater than minimal interference with sexual function	NA
Dysmenorrhea/cramping with menses	None	Pain causing no or minimal interference with usual social & functional activities	Pain causing greater than minimal interference with usual social & functional activities or the need for non-narcotic medication	Pain causing inability to perform usual social or functional activities or the need for narcotic medication

¹ If pain or tenderness is included in the grading of another category (e.g., PID), it should not be graded again in the pain or tenderness category

NOTE: For protocols utilizing this Addendum, when the same parameter appears in both this Female Genital Grading Table and the main DAIDS AE Grading Table, use the grading scheme in this table.

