6.5. Missing Data

The primary efficacy outcome measure of BV recurrence will be assessed in the CC population. Use of the mITT population has previously been recommended by the FDA where missing values from subjects who drop out early are imputed using Last Observation Carried Forward (LOCF) [6]. However, this includes subjects who dropped out after completing at least one-follow-up visit, and/or before their first positive diagnosis. LOCF would classify such subjects as ‘not recurrent.’ Thus, it is possible that the estimated proportions of treatment successes in a study arm could, in reality, be larger than expected. Thus, LOCF could result in an over-optimistic estimate of treatment effect, conflicting with the following rationale for using an ITT analysis population stated in ICH E9 [7]: “[ITT analysis] tends to avoid over-optimistic estimates of efficacy resulting from a per protocol analysis, since the non-compliers included in the [ITT] analysis set will generally diminish the estimated treatment effect.” In addition, simulation studies suggest that CC analysis leads to slightly less biased estimates of the difference in cure proportions (LACTIN-V vs. placebo) compared to the mITT analysis using LOCF.

To assess the effect of the choice of analysis population on the primary analysis, the analysis will be repeated as a secondary analysis in the ITT, mITT, and PP populations. The following imputation methods will be used for BV recurrence by Visit 4 and BV recurrence by Visit 7 in the ITT and mITT populations:

- LOCF
- Worst-Case Scenario – impute missing/unevaluable values in the LACTIN-V group as treatment failures and missing values in the Placebo group as treatment successes.

For summaries of recurrence in “by study day” displays, missing data will not be imputed.

For the secondary analyses of successful *L. crispatus* colonization by Visit 4 and by Visit 7, missing or unevaluable colonization data at a visit will imputed as unsuccessful colonization. For summaries of colonization in “by study day” displays, missing data will not be imputed.

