Table 21 will present the proportion of subjects who experience successful *L. crispatus* colonization at any time post-baseline through Visit 4 (Week 12) (and 95% Wilson confidence interval) in each treatment group along with the odds ratio of *L. crispatus* colonization (and 95% asymptotic confidence interval). A formal hypothesis test will be performed with null hypothesis that the proportion subjects who experience successful *L. crispatus* colonization through Visit 4 (Week 12) in the LACTIN-V group is equal to that in the placebo group and alternative hypothesis that they are not equal. The p-value from the Chi-Square test will be presented. The analyses will be performed in the ITT, mITT, CC, and PP populations, where the ITT and mITT summaries will use the imputation methods described in Section 6.5. Table 22 presents the same summaries for successful *L. crispatus* colonization at Visit 7 (Week 24). Table 23, Table 24, Table 25, and Table 26 present *L. crispatus* colonization by study visit (and 95% Wilson confidence interval) in each treatment group along with the odds ratio of *L. crispatus* colonization (and 95% asymptotic confidence interval). A formal hypothesis test will be performed with null hypothesis that the proportion of subjects who experience successful *L. crispatus* colonization through each visit in the LACTIN-V group is equal to that in the placebo group and alternative hypothesis that they are not equal. The p-value from the Chi-Square test will be presented. Table 27, Table 28, Table 29, and Table 30 presents summary statistics of the concentration of *L. crispatus* CTV-05 by study visit.

Table 31, Table 32, Table 33, and Table 34 will present *L. crispatus* colonization by study day, treatment group, and number of condom-less sexual intercourse acts for each analysis population. The proportion of subjects with colonization along with the 95% Wilson confidence intervals will also be presented. Number of condom-less sexual intercourse acts will be broken up by quartiles from data obtained from the sexual history interview. If the distribution of sexual intercourse acts is such that the use of quartiles does not lead to distinct intervals of values, other cutpoints will be examined (e.g. tertiles, above/below median). Figure 10, Figure 11, Figure 12, and Figure 13 will present *L. crispatus* CTV-05 concentration by study visit, treatment group, number of condom-less sexual intercourse acts, and analysis population.

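### Protocol 7.9 omits the L. crispatus qPCR swab that Appendix A requires at discontinuation and early termination, and the SAP scores the resulting gap as no colonization in ITT and mITT

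*Protocol*

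**What the plan says.** Protocol 7.9 sets out the pelvic examination for a woman who stops product or ends participation early, as items a to h. After pH, wet mount and Gram stain come "f. Vaginal swabs (no more than two) for storage and future identification of vaginal bacteria, and possible multiomic" testing, then "g. If indicated, cervical (or vaginal) swab for nucleic acid amplification of" three sexually transmitted organisms, and last "h. Other tests as deemed necessary by the site investigator in response to symptoms presented at this visit". No item asks for the qPCR sample.

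The clinic-visit sections on either side of it do. Protocol 7.10 has "g. Vaginal swabs for *L. crispatus* identification with qPCR", and 7.2, 7.3, 7.5 and 7.8 carry the same line (7.4 by reference to 7.3).

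The row "Vaginal swab for qPCR" in Protocol Appendix A has a plain X under both Study Product Discontinuation and Early Termination. The legend keeps a bracketed X for procedures done only if indicated, so the plain X is unconditional. SAP Table 2 repeats the row.

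For the analysis, SAP 6.5 says that "missing or unevaluable colonization data at a visit will imputed as unsuccessful colonization" in the analyses by Visit 4 and by Visit 7. SAP 8.2 defines success for the first of these as "colonization at any time post-baseline through Visit 4 (Week 12"), and applies the 6.5 imputation to the ITT and mITT summaries. SAP 6.5 does not impute the by-study-day displays.

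**The concern.** Two sites can each follow the protocol and collect different data. A site using the schedule takes the swab at the last contact with a departing woman. A site using the visit text does not. One positive result is enough for success through Visit 4, so for some women this swab decides the outcome. Where it is not taken, the plan records a failure to colonize that reflects a missing line in the protocol and not the product.

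Colonization is a named secondary objective, and Protocol 2.1 and 2.2 present it as the way the product is expected to prevent recurrence. For women who leave, colonization status also helps to tell failure to colonize from departure for other reasons.

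**Working it through.** **Step 1: compare the lists.**

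| Place | qPCR swab |
|---|---|
| Protocol 7.2, 7.3, 7.5, 7.8, 7.10 (item g); 7.4 by reference | listed |
| Protocol 7.9, items a to h | not listed |
| Protocol Appendix A, qPCR row | plain X at Visits 1 to 4 and 7, unscheduled, discontinuation and early termination |
| SAP Table 2, qPCR row | same as Appendix A |

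**Step 2: see whether another item of 7.9 supplies the sample.** Item g is for sexually transmitted infections, if indicated. Item h depends on symptoms and the investigator's judgment. Item f collects storage swabs, but Protocol 14.7 makes storage optional with separate consent, and Protocol 8.2.2 ties testing of the stored specimen for other bacteria to outside funding. None of these is the scheduled qPCR swab.

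**Step 3: identify who is affected.** All of these must hold:
- she leaves the study before Visit 4 (a woman who only stops product is followed through Visit 7 under Protocol 5.3.4 and has qPCR at her remaining clinic visits);
- she attends a termination visit, which Protocol 5.3.4 only encourages;
- the site follows 7.9 and not Appendix A;
- she has no earlier positive post-baseline qPCR;
- the omitted swab would have been positive.

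She is then scored as not colonized in ITT. She is scored so in mITT too if she had a post-baseline visit. The SAP does not say whether a termination visit meets that condition.

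The Week 24 outcome is colonization at Visit 7, which an earlier termination swab would not normally supply. The gap therefore bears on the Visit 4 outcome.

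**Step 4: size.** The plan gives no figure for this gap. The denominator comes from the planned enrollment of 228 at 2:1: 228 × 2/3 = 152 LACTIN-V women. The 228 itself reproduces: 30% against 15%, two-sided 5%, 70% power, 2:1, no continuity correction gives 68 + 136 = 204; 204/0.90 = 226.7, so 227, and 228 to fit 2:1. The concern does not touch it.

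Let k be the number of LACTIN-V women who meet the first four conditions, and q the share of them who would have tested positive. Then

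understatement in percentage points = 100 × k × q / 152.

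The documents give neither k nor q. For q, two earlier ITT colonization rates in Protocol 2.1 serve as assumptions: 61% (Phase II-a, 4 weeks) and 42% (capsule trial, 4 months). Neither describes women who leave early.

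| k (assumed) | q = 1 | q = 0.61 | q = 0.42 |
|---|---|---|---|
| 1 | 1/152 = 0.7 | 0.61/152 = 0.4 | 0.42/152 = 0.3 |
| 5 | 5/152 = 3.3 | 3.05/152 = 2.0 | 2.10/152 = 1.4 |

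**The case against.** The best reply is that this is a slip between a visit list and a schedule, with little riding on it. SAP 6.1 makes Complete Case the primary population for every efficacy outcome. SAP 6.3.2.3 excludes from it women who terminate early for reasons other than lack of effect and have no positive BV result. The imputation reaches only ITT and mITT. Any earlier positive swab already counts, and the words on success at any time through Visit 4 arguably admit a termination-visit result as they stand.

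Most of this stands, and it limits the size of the point. It does not remove the contradiction, because nothing in 7.9 tells a site to take the swab. Complete Case is not wholly immune: a woman whose first BV diagnosis is made at her termination visit can belong to it without a qPCR result from that visit. The SAP wording also leaves room for doubt. Section 6.5 speaks of data missing at a visit, and the window rule in section 4.5 covers several observations within one visit period, not the assignment of a termination result to Visit 4.

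A reader might infer three stronger things that the documents do not support:
- **A loss of 6 points or more.** Taking 10% of 152 as 15 women at 61% gives 15 × 0.61/152 = 6.0 points. That is not a ceiling, since 15/152 is 9.9 points, and it is not a likely value. The 10% in the sample-size section is total drop-out from Complete Case. It can include loss to follow-up and missing Amsel or Nugent results. The 6 points need all 15 to leave before any other post-dose swab, attend a termination visit and go unswabbed.
- **That colonization status is lost for every woman who stops product.** Those who stay in the study keep their scheduled swabs.
- **That applicator staining is missing in the same way.** Item 8 of 7.9 says "Applicators used since the last study visit will be collected. Any remaining unused applicators will also be collected" and does not mention staining. But Protocol 6.3 already provides that used applicators are stained. The staining row of Appendix A, as extracted, has a single entry at Visit 2, marked as site discretion, and none for these visits. SAP 3.3.5 uses self-report where a kit is missing, incomplete or indeterminate.

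**Conclusion.** The contradiction between Protocol 7.9 and Appendix A (with SAP Table 2) on the qPCR swab is real, and SAP 6.5 turns the missing sample into a failure. The consequence is narrow: the ITT and mITT analyses of colonization through Visit 4, for women who leave before Visit 4, attend a termination visit and have no earlier positive result.

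Each such woman who would have tested positive costs the LACTIN-V proportion about 0.7 points, given 152 women in that arm. Their number is unknown, and the chain of conditions makes a large total unlikely. The sample size, the primary BV analysis and the by-study-day displays do not depend on it, and Complete Case depends on it little. The point merits correction because the direction of the error is known, a missed swab cannot be recovered, and the remedy is slight.

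**What to change.** **Protocol 7.9:** add to the pelvic-exam list the line that 7.10 carries as "g. Vaginal swabs for *L. crispatus* identification with qPCR", so that the text agrees with Appendix A and SAP Table 2.

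**SAP 6.5 and 8.2:** state that an evaluable qPCR result from a discontinuation or early-termination visit, up to the end of the Visit 4 window, counts toward colonization through Visit 4 before any imputation.

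No change to applicator staining is needed on this ground.

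The cost is one line in the protocol and one sentence in the SAP. The swab is already in the schedule of events, so no procedure is added. The protocol line helps only termination visits still to come. The SAP sentence also covers results already collected by sites that followed Appendix A.

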7.10 Unscheduled Visit

An unscheduled visit following a participant's request or the site investigator's recommendation should be recorded on the appropriate CRF. The following procedures and assessments may be performed at the unscheduled visit:

1. Staff will review the memory aid with the participant. The participant will be asked about symptoms, concomitant medications and any medical problems since the last visit, which will be recorded on the appropriate CRF. Additionally, the participant will be asked to provide exact dates and times of the study product administration.
2. Medical, gynecological and sexual history to include assessment of STI and HIV risk
3. Symptom-directed physical and pelvic examination by a study physician or nurse that will include vital signs, including temperature, and examination of respiratory and cardiovascular systems, as well as assessment of symptoms and adverse events
4. The pelvic examination will be conducted in the following order:
 - a. Examination of the external genitalia
 - b. Speculum insertion and examination of vagina, fornices and cervix with naked eye. Water will be used to ease speculum insertion. No lubricant should be used as it could contain chlorhexidine which may kill *Lactobacillus*.
 - c. Vaginal pH
 - d. Vaginal swab for wet mount taken from the posterior fornix for yeast vaginitis and clue cells and for amine test (whiff test)
 - e. Vaginal swab for Gram stain (Nugent scoring system)
 - f. Vaginal swabs (no more than two) for storage and future identification of vaginal bacteria, and possible multiomic (e.g. proteomics, metabolomics, etc.) testing
 - g. Vaginal swabs for *L. crispatus* identification with qPCR
 - h. If indicated, cervical (or vaginal) swab for nucleic acid amplification of *N. gonorrhoeae*, *C. trachomatis*, and *T. vaginalis*
 - i. Other tests as deemed necessary by the site investigator in response to symptoms presented at this visit
5. If indicated, clean catch urine dipstick; urinalysis if abnormal results indicate
6. If indicated, β hCG pregnancy test
7. All clinical and laboratory findings at the time of the evaluation will be recorded on the CRF. These findings will include observations present on the pelvic exam such

- as genital findings including location; presence or absence, and character of vaginal or cervical discharge or lesions; and results of any on-site tests.
8. The applicators used since the last study visit will be collected. Applicators will be stained and tested as described in the MOP.
 9. An additional unscheduled visit as deemed necessary by the site investigator to ensure short-term surveillance will be planned.
 10. If the site investigator decides together with the participant that study product use can continue, participants will be asked if they still have the remaining applicators for the twice weekly doses stored at home. If not, they will receive additional pre-filled applicators to administer twice weekly through week 11. Participants will be instructed to transport the pre-filled applicators while avoiding exposure to high temperatures.
 11. Participants will be reminded not to use scented tampons or any other vaginal products through Visit 7 (Week 24, Day 168).
 12. Participants will be reminded to abstain from sexual intercourse for 12 hours after each study product application and 12 hours before the remaining study visits.
 13. Participants will receive non-spermicidal lubricated condoms for their male sexual partners. Participants will be encouraged to use condoms if they engage in vaginal intercourse through Visit 7 (Week 24, Day 168).
 14. Participants will be instructed to collect all used applicators and store them as described in the MOP and to return all used applicators at their next visit.
 15. An appointment for the next regular follow-up visit will be scheduled. Depending on the time of the enrollment and the average length of the participant's menstrual cycle, careful attention should be paid to the approximate time of the participant's next menstrual period when scheduling those visits. Later adjustments of those dates may be necessary.

Women with vaginal discharge or vaginitis symptoms who were diagnosed with yeast on the wet mount during the follow-up visit will be referred for standard treatment and continue to receive study product.

If the test results at the follow-up visit suggest a urinary tract infection, cervicitis or vulvovaginitis, the participant will be referred for standard treatment and continue to receive study product.

If the clinician suspects the woman to have developed an STI since the last visit, appropriate tests will be conducted and if needed the woman will be referred to standard of care treatment in compliance with current CDC STD Treatment Guidelines. The participant should be treated in case of positive findings and continue to use study product.

Women who develop *symptomatic* BV confirmed by wet mount Amsel criteria ≥ 3 (with or without confirmatory Gram stain) at least 4 weeks after the last MetroGel treatment will be retreated with MetroGel. This practice follows CDC treatment guidelines and FDA recommendations. The 5-day course of MetroGel will begin as soon as possible. Women will skip their regularly scheduled dose of study product until 24 hours after their last dose of MetroGel when study product dosing will continue twice weekly. Women diagnosed with *asymptomatic* BV during the follow-up visit will not be retreated with MetroGel.

